6.4.4 Subgroup analysis

The time to event analysis for the safety variable (composite of major bleeding (MB) and clinically relevant non-major bleeding (CRNMB) events, as assessed by CIAC) will be repeated by the following subgroups:

- Age group 1 (<60 years, 60-75, >75years)
- Age group 2 (<50yrs/>=50-<60yrs/>=60-<65yrs/>=65-<70yrs/>=70-<80yrs/>=80yrs)
- Sex (male, female)

- Patients with AF (Yes/No)
- Patients with diabetes mellitus
- Patients with prior CV events (Stroke, TIA, MI, DVT, PE) (Yes/No)
- Patients with prior MACE
- Patients with ASA / non-ASA
- History of (symptomatic) COVID-19 (Yes/No)
- Symptomatic COVID-19 during the study (Yes/No)

Forest plots showing incidences and hazard ratios will be provided for the comparison of high dose osocimab and placebo and low dose osocimab and placebo, respectively.

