Treatment: Low/high-dose osocimab or matching placebo on top of standard of care

Intercurrent events: Of interest is the response to treatment while the subject is

- alive (intercurrent event “death”) and
- exposed to assigned treatment (intercurrent event “premature discontinuation of treatment”. Rationale: The primary objective is to assess the safety under an osocimab concentration which is expected to be maintained during a chronic treatment.),

i.e. both intercurrent events are handled using the same strategy “while alive” or “while on treatment”.

Changes in the background therapy etc. will be handled following the treatment policy strategy. Other potential intercurrent events are not anticipated.

Population-level summary: (Cause-specific) hazard ratios comparing each of the osocimab dose groups with the placebo group as estimated from cause-specific Cox proportional hazards models.

Of note, based on the current expert assessment of the COVID-19 Public Health Emergency, it was to be expected that a low number of patients will suffer from (symptomatic) COVID-19. In addition, as ESRD patients visit dialysis centers on a regular basis anyway, no increase in missing data is to be expected. This is why no intercurrent event linked to the COVID-19 Public Health Emergency was accounted for. However, any premature discontinuation will be summarized, and selected analyses will be repeated by (symptomatic) COVID-19 (Yes/No). Also, if occurred, number of missed visits related to the COVID-19 pandemic will be summarized.

3. Study Design

Study 20115 is a covariate-adaptive randomization, double-blind, parallel group, placebo controlled, multi-center study to assess the safety and tolerability of monthly administrations of a low and high dose cohort of osocimab given subcutaneously in ESRD patients on hemodialysis. Here the term hemodialysis includes hemodiafiltration. The overall study design is depicted in the figure below.

Approximately 600 subjects (up to 750) from approximately 150 sites are planned to be randomized and will receive either osocimab (200 subjects on each dose arm), or placebo (200 subjects, i.e. 100 subjects receiving low dose volume placebo and 100 subjects receiving high dose volume placebo).

The following regions are planned to be included: North America, Europe, Asia Pacific.

The planned study will consist of:

- Screening period (visit 1): up to 14 days

- Randomization (visit 2): 1 day

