- Pre-treatment period (from visit 2 until visit 4): 7 days
- Main treatment period (from visit 5 until EOMT visit): 6 months
- Extension treatment period (from visit 19 until EOET visit): up to 12 months
- Follow-up period (from visit 32 until visit 35): 4 months after end of treatment (EOMT or EOET)

Informed consent form will be obtained at the beginning of the screening period. During the screening period, subject's eligibility evaluations will be performed. Subjects will be randomized either to osocimab or to placebo using a covariate-adaptive randomization technique (minimization methods) (for details see Section 6.3).

During the pre-treatment period, which will serve as a baseline period, a series of 3 hemodialysis sessions will be performed. Unfractionated or low molecular weight heparin (UFH/LMWH) is allowed as anticoagulation for maintenance of hemodialysis treatment during the whole study duration.

The study intervention will be administered subcutaneously abdominal with one single loading dose at visit 5 and monthly maintenance doses from visit 8 onwards until the end of the extension treatment period with an overall maximum of 18 months of treatment. The main treatment period consists of 6 months of treatment as this time frame is deemed to be the minimum clinically relevant treatment time to assess osocimab as chronic life-time treatment in an appropriate manner and in preparation for Phase 3.

Study intervention will be administered during the extension treatment period for up to a maximum of 12 months or until the last subject randomized to the study has performed the EOMT visit (whichever comes first).

The treatment period (main or extension) will end with the study assessments performed 30 days after the last study intervention administration.

The follow-up period is an observational period of 4 months, i.e. ends approximately 5 months after the administration of the last dose of osocimab.

[figure not shown]
All suspected bleeding and cardiovascular (CV) or thromboembolic (TE) events occurring after signing informed consent (randomized subjects only) will be adjudicated by the CIAC in a blinded fashion; blinded to treatment allocation and dose cohort (details are described in the CIAC charter).

The procedures followed by the CIAC are detailed in the CIAC charter. Detailed instructions regarding documentation, reporting and transfer of adjudication dossiers will be provided in a study specific guidance document.

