6.4 Safety

6.4.1 Primary safety variables

The composite of major bleeding (MB) and clinically relevant non-major bleeding (CRNMB) events, as assessed by CIAC, and the composite of moderate and severe AEs and SAEs will

be the primary safety endpoints in this study. Only events that started after the first dose of study treatment and during the main treatment period are considered for the primary analysis.

For the primary safety analysis descriptive time to first primary safety event (both treatment emergent AEs and composite of treatment emergent major and CRNMB events [in alignment with ISTH guidelines]) analyses will be performed.

According to the description of the primary estimand, the following events will be considered as competing events for the respective safety endpoint:

- death
- premature end of exposure to assigned treatment (last administration of assigned treatment plus 30 days).

For the primary analysis, the time to event for a subject will be censored at the date of the EOMT visit or after no further data collection happened for a subject (e.g. lost to follow-up).

According to the study protocol (section 7.1.1) one maintenance dose can be missed. If a subject misses a maintenance dose, has a so called administration gap, that lasts longer than 30 days, the subject is not considered at risk for treatment-emergent events during this time until the next dose. When the subject then takes a maintenance dose again, he/she is at risk again. Accordingly there will be additional analyses, where the time not under exposure between two doses will be ignored and events during that time will not be counted. The time under risk will be calculated by removing time between the interrupted dose + 30 days and the next dose and the time more than 30 days after permanent discontinuation to study drug and if occurred the 1st event per patient will be counted. For the primary analysis in this data scope, the time to event for a subject will be censored at the date of the EOMT visit or after no further data collection happened for a subject (e.g. lost to follow-up).

The cumulative incidence function for the event-of-interest as well as the associated competing event(s) together with the corresponding confidence interval will be estimated for each treatment arm using Aalen-Johansen estimators.

The competing event for the primary safety endpoint is death and premature discontinuation of exposure to assigned treatment.

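### Splitting time-to-event results by COVID-19 during the study groups participants by a later event: the subgroup incidences are biased, most for fatal outcomes, though the consequence is minor

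*SAP*

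**What the plan says.** - SAP 6.4.4 repeats the analysis of major and clinically relevant non-major bleeding by ten subgroup factors. One is "Symptomatic COVID-19 during the study (Yes/No". SAP 6.2.4 lists the same factor for the efficacy variables.
- Both lists also contain a separate baseline factor, "History of (symptomatic) COVID-19 (Yes/No".
- The output is stated: "Forest plots showing incidences and hazard ratios will be provided", for each dose against placebo.
- SAP 2 sets no COVID-19 intercurrent event, expects a low number of symptomatic cases, and says that "selected analyses will be repeated by (symptomatic) COVID-19 (Yes/No".
- On the outcome window, SAP 6.4.1 says: "Only events that started after the first dose of study treatment and during the main treatment period are considered for the primary analysis". The Cox model there contains treatment group only, with time counted from first administration.
- SAP 3 gives the length of that window: "Main treatment period (from visit 5 until EOMT visit): 6 months". The same list then allows at most 12 further months on treatment, and 4 months of observation once treatment has stopped. A participant can thus be in the study for up to 6 + 12 + 4 = 22 months from first dose. One with no extension has 6 + 4 = 10.
- Neither document gives a landmark, a time-dependent COVID-19 covariate, a rule that infection must come before the outcome, or an end date for counting infections.

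**The concern.** Every other factor in the two lists can be read as a baseline characteristic. This one is settled after randomisation but applied from first dose, which causes two problems.

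First, a Yes participant must have survived and stayed in the study until infection. The time before infection is immortal for any outcome that ends participation. Second, a non-fatal outcome can come before the infection that defines the group, so it may be displayed as an event in a COVID-19 patient although it happened before COVID-19.

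SAP 2 handles COVID-19 through this split instead of through the estimand. A reader of the forest plots could therefore take a difference created by the classification as an effect of infection, or take the Yes-group hazard ratio as the effect of osocimab in infected patients.

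**Working it through.** The SAP states no figure for this split, so there is none to reproduce. The check asks what the split would show if COVID-19 had no effect at all.

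**Inputs** (rates per patient-year)
- Bleeding b = 0.10 and drop-out l = 0.15: SAP 9.1.
- Outcome window T = 0.5 years: SAP 3 and 6.4.1.
- Death d = 0.10 and COVID-19 c = 0.10: assumptions; the documents give neither.
- Window W for counting infections: not stated. Two cases are shown: 0.5 years (matched to the outcome) and 1.75 years (21 months, near the 22-month maximum).

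All times are exponential and independent. Write m = d + l = 0.25.

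**1. Fatal outcome**

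Yes deaths per person = d × [(1 − e^(−mT))/m − (1 − e^(−(m+c)T))/(m+c)] = 0.1 × [0.47001 − 0.45869] = 0.00113.

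All deaths = 0.1 × 0.47001 = 0.04700, so No deaths = 0.04587.

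Yes person-years = (0.47001 − 0.45869) + c/(m+c) × [0.45869 − T × e^(−(m+c)W)].
- W = 0.5: 0.01132 + 0.2857 × (0.45869 − 0.41973) = 0.02245
- W = 1.75: 0.01132 + 0.2857 × (0.45869 − 0.27100) = 0.06495

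No person-years = 0.47001 minus these: 0.44756 and 0.40507.

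| Infection counted over | Yes, deaths per 100 PY | No, deaths per 100 PY |
|---|---|---|
| 6 months | 0.00113/0.02245 = 5.0 | 0.04587/0.44756 = 10.2 |
| 21 months | 0.00113/0.06495 = 1.7 | 0.04587/0.40507 = 11.3 |

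The true rate is 10 in everyone. Varying COVID-19 from 5 to 20 per 100 PY in simulation gives about 5.0 v 10.1–10.5 (main period) and 1.7–1.8 v 10.6–13.0 (about 22 months).

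**2. Order of bleed and infection in the Yes group**

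Bleed first = b × c/(m+c) × [(1 − e^(−0.45T))/0.45 − e^(−0.35W) × (1 − e^(−0.1T))/0.1].
- W = 0.5: 0.02857 × (0.44774 − 0.40941) = 0.001095
- W = 1.75: 0.02857 × (0.44774 − 0.26433) = 0.005240

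Infection first = 0.1 × (0.45869 − 0.44774) = 0.001095.

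Share with bleed first: 0.001095/0.002190 = 50%, and 0.005240/0.006335 = 82–83%.

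**3. Bleeding rates**

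If bleeding is independent of infection, death and drop-out, the split is independent of bleeding and both groups show 10 per 100 PY in either window. A difference needs an added link. In simulation:
- A bleed raises death 3- to 5-fold: the Yes rate is 11–21% below the No rate with 21 months, and 0–2% below with 6 months.
- A bleed triples later infection risk: the Yes rate is about 2.7 times (21 months) or 2.05 times (6 months) the No rate.

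**4. Between-arm hazard ratio for bleeding**

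With infection tripled after a bleed and 21 months, a true ratio of 2.0 reads about 1.86 in the Yes group, a shift of 7%. That was the largest shift in the scenarios run.

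The ratio still does not measure the effect in infected people. Suppose it is 1 before infection and 3 after. Weighting by the shares in step 2, the Yes group shows about 0.50 × 1 + 0.50 × 3 = 2.0 or 0.83 × 1 + 0.17 × 3 = 1.3, depending only on the window.

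**5. Would the Yes-group ratio be shown?**

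Expected bleeds per 200-person arm = 200 × (0.10/0.25) × (1 − e^(−0.125)) = 9.4. With 5%, 10% or 20% of an arm infected, that is 0.47, 0.94 or 1.88 in the Yes group.

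SAP 6 requires at least 3 events in one arm and at least 1 in each compared arm. With Poisson counts the chance is [1 − P(0)]² − [P(1) + P(2)]², about 1%, 8% and 41%. This assumes that the rule is applied within subgroups.

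**The case against.** The strongest defence concerns size, and most of it stands.

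- **Window.** SAP 6 limits analyses at primary completion to the main treatment period. If that also limits which infections count, the windows match. No infection then falls after the outcome window, and the share of bleeds before infection is about 50%, not 82%. A reader might infer that most infections fall after the outcome window: under the 21-month assumption the share is (0.8395 − 0.5420)/(1 − 0.5420) = 65%. The documents do not fix that window, and participants with little or no extension have far less than 21 months.
- **Bleeding.** A reader might infer that the Yes and No bleeding rates must differ. They need not: without a link from bleeding to infection, death or retention they are equal, and the direction of any difference depends on the link assumed.
- **Hazard ratios.** A reader might infer that the between-arm ratios are badly distorted. The scenarios do not show this. The shift of up to about 7% is small beside the whole-trial 90% interval of 0.57 to 2.28 in SAP 9.1.
- **Consequence.** The study is descriptive with no formal hypothesis, this is one of ten factors, few cases are expected, and the minimum-event rule may suppress many Yes-group ratios.

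The defence does not rescue the split. Even with matched windows, half of the Yes-group bleeds precede infection and a fatal outcome reads at half its true rate. Neither subgroup section states the infection window, and SAP 6 brings in the extension and follow-up at study completion. The minimum-event rule is written for endpoints, without mention of subgroups.

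**Conclusion.** The split is wrong as written, and the point is minor. The subgroup incidences carry immortal-time and reverse-order bias, and the Yes-group hazard ratio has no meaning as an effect in infected participants.

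The distortion is clearest for fatal outcomes: about 5 v 10 per 100 PY (6 months) to 1.7 v 11 (21 months) when the truth is 10 in both. That calculation is for an outcome made up only of deaths. The composite in SAP 6.2.1 mixes vascular deaths with non-fatal events, so its distortion would be smaller.

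For bleeding, the problem is mainly one of interpretation. All sizes rest on assumed death and COVID-19 rates, constant over time, and on the two windows shown. The primary analysis of the whole safety set and the baseline COVID-19 history split are unaffected.

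**What to change.** - Remove the during-the-study COVID-19 factor from the incidence and hazard-ratio forest plots in SAP 6.2.4 and 6.4.4. Keep the baseline history factor.
- Align the sentence in SAP 2 that announces the repeat by COVID-19 status.
- In its place, report by arm the number of events before and after COVID-19 onset, with the period for counting infections stated.
- Use onset as a time-dependent covariate only if there are enough events. With about one expected Yes-group bleed per arm it would be barely estimable. Censoring at onset is possible but adds an independent-censoring assumption.
- Document the timing. SAP 6.5 indicates that the primary analysis is already complete, and SAP 4.4 treats later evaluation as open-label, so the change must be recorded as made after the primary analysis. Any output already produced for this factor should carry a caution.

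The cost is a SAP amendment and one replaced exploratory display. No new data are needed.

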6.4.5 Adverse events

The investigator has to record on the respective CRF pages all adverse events (AEs) occurring in the period between the signing of the informed consent and the end of the post-treatment follow-up period.

The original terms used by investigators to report AEs via the CRFs will be coded using the Medical Dictionary for Regulatory Activities (MedDRA). All reported adverse events during the main treatment period will be summarized by means of AE tables based on the treatment-emergent approach (see section 4.5).

All AE/SAE/AESI tables will also be provided for the following timeframe named “Full study TE AEs (SAE/AESI)”: AEs occurred after first intake of study intervention up to 5 months after last intake.

If an AESI will be reported, this will always be done separated for the two categories listed below.

For each AE, the number and percentage of subjects who experienced at least 1 occurrence of the given event will be tabulated according to the affected primary system organ class (SOC) and preferred term (PT) by treatment arm. A total column will be included in all safety summaries.

Frequency tables, showing an overall summary of number of subjects with AEs, serious adverse events (SAEs) and adverse events of special interest (AESIs) separated by the two categories will be given, and will include the following information.

- if the AE (/ SAE/AESI) occurred with causal relationship to study drug ,
- if the AE (/SAE/AESI) occurred with causal relationship to study procedures
- reasonable causal relationship to ESRD
- reasonable causal relationship to hemodialysis procedure
- maximum intensity for any AE
- maximum intensity for any study-drug related AE,
- AE related deaths.
- AE resulting in permanent discontinuation of study drug

The two categories of AESI are:

- Decrease in platelets below $75 \times 10^9/L$ or $> 50\%$ decrease in platelet count from baseline
- Hypersensitivity (i.e. any allergic reactions of \geq CTCAE criteria 2 [Common Terminology Criteria for Adverse Events] or anaphylaxis)

A similar table showing overall summary information of AEs (/SAE/AESI) during screening will be given.

Additionally, frequency tables summarizing infection site events will be provided for the SAF.

Injection site event is defined as any AE at the injection site presenting as Injection site erythema, Injection site swelling, Injection site pruritus, or Injection site pain that started on the day of injection.

In addition, frequency tables will summarize the number of subjects with any event occurring during pre-treatment period.

For the full analysis set the event which occurred during the extension treatment period and during the post treatment follow-up period will be considered.

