## 8.2.6 Clinical Safety Laboratory Assessments

- See Section 10.2 for the list of clinical laboratory tests to be performed and the SoA (Section 1.3) for timing and frequency.
- The investigator must review the laboratory report, document this review, and record any clinically relevant changes occurring during the study in the AE section of the eCRF. The laboratory reports must be filed with the source documents. Clinically significant abnormal laboratory findings are those which are not associated with the underlying disease, unless judged by the investigator to be more severe than expected for the participant's condition.
- All laboratory tests with values considered clinically significantly abnormal during participation in the study or until the end of study should be repeated until the values return to normal or baseline or are no longer considered clinically significant by the investigator or the medical monitor.
  - If such values do not return to normal/baseline within a period of time judged reasonable by the investigator, the etiology should be identified and the sponsor notified.
  - All protocol-required laboratory assessments, as defined in Section 10.2, must be conducted in accordance with the laboratory manual and the SoA.
  - If laboratory values from non-protocol specified laboratory assessments performed at the institution's local laboratory require a change in participant management or are considered clinically significant by the investigator (e.g., SAE or AE or dose modification), then the results must be recorded in the eCRF.
- Appropriate blood draws from the dialysis access for any type of blood sampling, collected from the hemodialysis line (not directly from the fistula, nor from any vein on the fistula arm), or tunneled catheters are permitted. Whenever possible, the blood should be drawn under the same conditions (details are depicted in the laboratory manual).
- Where possible for safety laboratory, pediatric-sized blood volumes (as opposed to adult-sized blood volumes) are to be taken and blood collections should be combined to minimize the number of needle punctures.
- During the screening visit, only local laboratory samples will be assessed to check the eligibility of the patient. For details see Section 10.2.

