### **8.3.8 Adverse Events of Special Interest**

Adverse events of special interest have to be reported to the sponsor along the timelines set for SAEs, i.e. within 24 hours of the investigator's awareness, as described in Section 8.3.1.

Declaration of an event as serious should only occur if one or more of the serious criteria is applicable. Non-serious adverse events of special interest should not automatically be upgraded to serious by the reporting investigator.

Adverse events of special interest are:

- Decrease in platelets below  $75 \times 10^9/L$  or  $> 50\%$  decrease in platelet count from baseline
- Hypersensitivity (i.e. any allergic reactions of  $\geq$  CTCAE criteria 2 [Common Terminology Criteria for Adverse Events] or anaphylaxis)

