**Table 10–1: Protocol-required Laboratory Assessments**

Laboratory Assessments	Parameters
Central laboratory	
Hematology	Hemoglobin Hematocrit Red blood cell (RBC) count (MCV, MCH, MCHC, %reticulocytes) Platelet count White blood cell (WBC) count with differential (neutrophils, lymphocytes, monocytes, eosinophils, basophils)
Clinical chemistry	Alanine aminotransferase (ALT) Albumin Alkaline phosphatase Amylase Aspartate aminotransferase (AST) Bicarbonate Bilirubin, total and direct Blood urea nitrogen (BUN) Calcium Chloride Cholesterol [high density lipoprotein (HDL), low density lipoprotein (LDL), total] Creatinine Creatine kinase (CK) Glucose Gamma glutamyl transpeptidase (GGT) high-sensitivity C-reactive protein (hs-CRP) Highly sensitive serum beta human chorionic gonadotropin ( $\beta$ hCG) Iron saturation and ferritin Lactate dehydrogenase (LDH) Lipase Magnesium Parathyroid hormone (PTH) Phosphorus Potassium Serum glutamic-oxaloacetic transaminase (SGOT) Serum glutamic-pyruvic transaminase (SGPT) Sodium Total protein Triglycerides Troponin Uric acid
Coagulation parameters should not be reviewed by blinded staff.	
Coagulation	Activated partial thromboplastin time (aPTT) Prothrombin time (PT), seconds and INR (International normalized ratio) D-Dimer

Laboratory Assessments	Parameters
Local laboratory	
Screening Tests	
Highly sensitive serum beta human chorionic gonadotropin (<math>\beta</math>hCG) pregnancy test (as needed for women of childbearing potential)
 
All study-required laboratory assessments for eligibility will be performed by a local laboratory:
 
Activated partial thromboplastin time (aPTT)
 
Prothrombin time (PT)
 
Bilirubin (direct, total)
 
Alanine aminotransferase (ALT)
 
Hemoglobin
 
Platelet count
 
The results of each test must be entered into the electronic case report form.

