6.4.7 Laboratory parameter

Only centrally analyzed blood samples will be considered for analysis.

Central laboratory parameters will be displayed by means of descriptive statistics and change from baseline by visit and treatment group. High/low abnormalities by laboratory parameter will be presented. This includes various hematology (white blood cell count (WBC), red blood cell count (RBC), ...), clinical chemistry (aspartate aminotransferase (AST), alanine aminotransferase (ALT), ...) and urinalysis (color, appearance, specific gravity, ...) parameters.

All duplicates at the same visit will be excluded from the statistical analyses in section 14 by programming algorithm, and they will be listed only in section 16.2.

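### The platelet AESI is tabulated from investigator-recorded events, and no planned table counts participants who meet its numeric thresholds in the central platelet data

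*SAP*

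**What the plan says.** Protocol 8.3.8 and SAP 6.4.5 define the platelet AESI in the same way: below 75 x 10^9/L, or a more than 50% "decrease in platelet count from baseline". Protocol 8.3.8 makes reporting compulsory: "Adverse events of special interest have to be reported to the sponsor along the timelines set for SAEs", that is, within 24 hours of the investigator's awareness.

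SAP 6.4.5 takes adverse events from the investigator's CRF entries, codes the investigator's terms in MedDRA, and tabulates them. For AESIs it adds: "If an AESI will be reported, this will always be done separated for the two categories listed below". It gives no rule for deriving the platelet category from laboratory values.

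SAP 6.4.7 uses central samples only. It plans descriptive statistics and change from baseline by visit and treatment group, and then: "High/low abnormalities by laboratory parameter will be presented". Under SAP 4.1 the descriptive statistics include the minimum, quartiles and maximum. Platelet count is among the central hematology tests in Protocol Table 10–1, and Tables 1–1 and 1–2 schedule those tests repeatedly, less often in the extension.

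For laboratory findings in general, Protocol 8.2.6 asks investigators to record clinically relevant changes and says: "Clinically significant abnormal laboratory findings are those which are not associated with the underlying disease". That sentence goes on to except findings judged more severe than expected. Protocol 10.3.1 likewise makes a laboratory abnormality an AE on the investigator's judgement of clinical significance.

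**The concern.** An event defined by two numbers can be counted by program from the platelet values. The plan instead relies on the site to see the result, compare it with a baseline, recognise that it qualifies, and file it. The below-75 criterion is easy to spot. The 50% criterion is not, because a qualifying count may look unremarkable on its own.

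Thrombocytopenia is one of the named risks in Protocol Table 2–1, where AESI reporting and laboratory monitoring are listed as mitigations. If qualifying falls go unreported, the AESI rate is too low and may vary between sites, while the values that would show this are already held. Few such events would be expected per arm, so a handful of missed cases could change how an arm looks.

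**Working it through.** The plan states no expected rate for this AESI, so there is no figure to reproduce. All counts below are x 10^9/L.

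**Inputs.** AESI thresholds: 75 and a more than 50% fall (Protocol 8.3.8, SAP 6.4.5). Eligibility floor: 100 (Protocol 5.2). Recovery level: 100,000/mm³, which equals 100 (Protocol 8.3.8.1). Planned arm size: 200 (Protocol 4.1).

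**Step 1: where the two criteria separate.** For baseline B, a fall of more than 50% means a count below B/2. It is reached before 75 when B/2 > 75, so B > 150. A qualifying count can exceed 100 when B/2 > 100, so B > 200.

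| Baseline B | B/2 | Counts qualifying by the 50% criterion alone |
|---|---|---|
| 150 | 75 | none |
| 180 | 90 | 75 to <90 |
| 200 | 100 | 75 to <100 |
| 250 | 125 | 75 to <125 |
| 300 | 150 | 75 to <150 |

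Example: (260 − 120)/260 = 53.8%. The count of 120 meets the definition but lies above both 75 and 100.

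**Step 2: what the planned laboratory output would show.** The change of 120 − 260 = −140 enters the change-from-baseline summary for that visit and, if it is the largest fall, appears as the minimum. If change is shown in absolute units, that does not identify an AESI: 400 to 260 is also −140 but is a fall of 140/400 = 35%. The low flag does not identify one either. The documents give no lower limit of normal. If it is 130 to 150 (an assumption), 120 is flagged low alongside minor deviations. With a baseline above 260 (limit 130) or above 300 (limit 150), a qualifying count can carry no flag. For example, 320 to 155 is 165/320 = 51.6% and is unflagged under either limit.

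**Step 3: dependence on the baseline sample.** A count of 120 qualifies only if the baseline exceeds 120/0.5 = 240. Protocol 4.1 calls the pre-treatment period the baseline period, and SAP 4.5 takes the mean if there is more than one measurement. Neither tells a site whether to use the local screening count, a central pre-dose count, or a mean. A participant whose candidate values straddle 240 would be a case under one choice and not under another.

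**Step 4: how many participants this could concern (assumption only).** Take baselines as normal with mean m of 180 to 240 and SD s of 50 to 70, truncated at 100. The share above c is [1 − Φ((c − m)/s)] / [1 − Φ((100 − m)/s)]. This gives 76% to 97% above 150 and 37% to 79% above 200. Under these assumptions the 50% criterion is the first one reached for most participants.

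**Step 5: why small losses matter (assumption only).** If a proportion p of a 200-participant arm truly qualifies and a fraction r is reported, the expected count is 200pr and the chance of seeing none is (1 − pr)^200.

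| p | True cases | Chance of none, r = 1 | r = 0.75 | r = 0.5 |
|---|---|---|---|---|
| 1% | 2 | 13.4% | 22.2% | 36.7% |
| 2% | 4 | 1.8% | 4.9% | 13.4% |
| 3% | 6 | 0.2% | 1.1% | 4.9% |

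Neither p nor r is in the documents. The table shows sensitivity and does not estimate a miss rate.

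**The case against.** The strongest reply is that sites cannot simply ignore these falls. Protocol 8.3.8 names the thresholds as AESIs with no clinical-significance condition, so the specific text can be read as overriding the general filter in 8.2.6 and 10.3.1. Protocol 8.3.8.1 requires a repeat measurement before further dosing when either threshold is met, so a compliant site must already do the 50% calculation; the 260-to-120 fall triggers it. Investigators must document review of each laboratory safety report (Protocol 10.2), platelets are not among the results withheld from sites (Protocol 8.2.6), and Table 2–1 has the DMC reviewing laboratory results. Alerts or reconciliation may exist in the laboratory manual, Monitoring Plan or DMC charter, which were not available. Investigators are blinded to active drug versus placebo, so missed reports should be largely non-differential within a dose cohort.

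Most of this stands, and it rules out stronger readings that a reader might infer:

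- That reporting is left to the investigator's discretion. Protocol 8.3.8 makes it compulsory; what remains is a tension with general text that the protocol does not resolve.
- That a qualifying fall would show only as a low flag. It also enters the change-from-baseline distribution.
- That the protocol has no baseline. Protocol 4.1 names a baseline period; what is missing is the sample or samples to use.
- That SAP 6.4.5 expressly excludes laboratory derivation. The AESI sentence is a display rule; reliance on investigator records follows from the rest of that section and from the absence of a derivation in 6.4.7.

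None of these safeguards puts a threshold-based count by arm into the report. Non-differential under-reporting would still lower the count in each arm.

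**Conclusion.** The gap is real but limited. The platelet AESI is counted from investigator-recorded events, and no planned table counts participants who meet its thresholds in the central data. Qualifying falls to counts above 75, or above 100 when the baseline exceeds 200, could go unreported, and the planned summaries would not count them as qualifying. It would be wrong to conclude that the AESI is in fact under-counted: the documents give no miss rate, and the illustrations in Steps 4 and 5 rest on assumed baselines, event rates and reporting fractions. The point affects the description of a named safety risk. It leaves the primary endpoints and the sample size unchanged. It is worth acting on because the remedy is cheap and the thresholds are already fixed in the protocol.

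**What to change.** Add to SAP 6.4.7, as a supplement to the investigator-reported AESI:

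- A table by treatment group of the number (%) of participants with any post-dose central platelet count below 75 x 10^9/L, or more than 50% below baseline. Show each criterion and either one, for the treatment-emergent window (to 30 days after the last dose) and the full-study window (to 5 months) in SAP 4.5.
- A named baseline: the SAP 4.5 mean of the central pre-dose platelet values, with the visits listed.
- Separate counts for any single value and for values confirmed on repeat. State how unscheduled repeats are kept, since SAP 6.4.7 drops duplicates at the same visit.
- A cross-tabulation against reported platelet AESIs, with a listing of discordant cases.

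The cost is one table and one listing from data already held. SAP 4.5 allows additional analyses and 4.6 allows an amendment or supplement. SAP 6.5 indicates that the primary analysis is complete, so the table should be labelled as added afterwards, with thresholds taken unchanged from the protocol.

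Limits: local counts are outside the SAP 6.4.7 analysis, and central sampling is sparse in the extension, so the derived count is not a reference standard there. Some discordance may come only from a site having used a different baseline sample. No dosing rule changes.
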